APPENDIX B: TOXICITY GRADING SCALE (cont'd)

EVENT	MILD (Grade 1)	MODERATE (Grade 2)	SEVERE (Grade 3)	POTENTIALLY LIFE THREATENING (Grade 4)
Neutrophils decreased	1500 – 2000 cells/mm ³	1000 – < 1500 cells/mm ³	500 – < 1000 cells/mm ³	< 500 cells/mm ³
Platelets	125,000 – 140,000 cells/mm ³	100,000 – < 125,000 cells/mm ³	25,000 – < 100,000 cells/mm ³	< 25,000 cells/mm ³
Liver function tests (AST, ALT)	1.1 – 2.5 × ULN	> 2.5 – 5.0 × ULN	> 5 – 10 × ULN	> 10 × ULN
Alkaline phosphatase	1.1 – 2.0 × ULN	> 2 – 3.0 × ULN	> 3 – 10.0 × ULN	> 10 × ULN
Albumin	2.8 – 3.1 g/dL	2.5 – < 2.8 g/dL	< 2.5 g/dL	—
Bilirubin – with increased LFTs	1.1 – 1.25 × ULN	> 1.25 – 1.5 × ULN	> 1.5 – 1.75 × ULN	> 1.75 × ULN
Bilirubin – with normal LFTs	1.1 – 1.5 × ULN	> 1.5 – 2.0 × ULN	> 2.0 – 3.0 × ULN	> 3.0 × ULN
Sodium – Hyponatremia	132 – 134 mEq/L	130 – < 132 mEq/L	125 – < 130 mEq/L	< 125 mEq/L
Sodium – Hypernatremia	144 – 145 mEq/L	> 145 – 147 mEq/L	> 147 – 150 mEq/L	> 150 mEq/L
Potassium – Hyperkalemia	5.1 – 5.2 mEq/L	> 5.2 – 5.4 mEq/L	> 5.4 – 5.6 mEq/L	> 5.6 mEq/L
Potassium – Hypokalemia	3.5 – 3.6 mEq/L	3.3 – < 3.5 mEq/L	3.1 – < 3.3 mEq/L	< 3.1 mEq/L
Blood Urea Nitrogen (BUN)	23 – 26 mg/dL	> 26 – 31 mg/dL	> 31 mg/dL	Requires dialysis
Serum creatinine	1.5 – 1.7 mg/dL	> 1.7 – 2.0 mg/dL	> 2.0 – 2.5 mg/dL	> 2.5 mg/dL or requires dialysis
Urine protein	Trace	1+	2+	Hospitalization or dialysis
Urine glucose	Trace	1+	2+	Hosp. for hyperglycemia
Urine blood (RBC/hpf) ^b	1–10 (clean catch, not menstruating)	11–50 (clean catch, not menstruating)	> 50 and/or gross blood	Hospitalization or packed red blood cells (PRBC) transfusion
	1–10 (clean catch, F)	11–50 (clean catch, F)		
	1–10 (M)	11–50 (M)	> 50 and/or gross blood	

LLN = Lower limit of normal. ULN = Upper limit of normal. ^bA positive test for blood will not be considered Clinically Significant in a female subject who is menstruating, and microscopic analysis will not be performed unless clinically indicated. If the subject is not menstruating a repeat Urine Analysis will be performed.

When developing this Toxicity Grading Scale, Emergent referred to the recommendations in the FDA's Guidance for Industry: Toxicity Grading Scale for Healthy Adult and Adolescent Subjects Enrolled in Preventive Vaccine Clinical Trials (2007) and adjusted some parameters to close gaps between the toxicity grades.

12 ATTACHMENTS

- 12.1 Study Personnel Roles and Responsibilities**
- 12.2 Recruitment Materials and Scripts**
- 12.3 Consent to Participate in Research for WRAIR CTC**
- 12.4 Consent to Participate in Research for USAMRIID Division of Medicine**
- 12.5 Consent for HIV Antibody Blood Test**
- 12.6 Information Sheet Regarding Compensation of Federal Personnel**
- 12.7 Active Duty Military Personnel Statement of Supervisor's Approval**

1. INTRODUCTION

1.1. Background

1.1.1. Chikungunya Virus and Chikungunya Fever

Chikungunya virus (CHIKV) is an arthropod-borne alphavirus of the family Togaviridae. As of May 29, 2018, over 80 countries or territories have documented cases of CHIKV infection excluding those countries where only imported cases have been documented. Although mosquitoes are the primary mode of transmission of CHIKV, blood-borne transmission via needle stick is possible. Maternal-fetal transmission has been documented during pregnancy (Staples 2017). Following an incubation period of 2 to 12 days, acute clinical manifestations include high fever, rash, gastrointestinal complications, headache, muscle pain, nausea, fatigue, myalgia, and joint pain (Borgherini 2007, Taubitz 2007, Pialoux 2007). The most classic symptom of chikungunya is a debilitating polyarthralgia that is present in greater than 90% of cases. This acute phase resolves within several weeks, but joint pain and arthritis may persist for months or years in over 30% of infected individuals (Schilte 2013).

There are currently no approved vaccines to prevent CHIKV infection or disease. However, protection against subsequent infection has been shown to correlate with the presence of anti-CHIKV antibodies that neutralize the virus in vitro (Yoon 2015). Such antibodies are readily induced by this and other vaccine candidates. But a major challenge stands in the way of licensing any chikungunya vaccine: the virtual impossibility of conducting a field efficacy trial, because outbreaks of chikungunya are so sporadic and short-lived. From the time the first case is detected until the epidemic begins to subside is often less than two months (Beesoon 2008).

1.1.2. Venezuelan Equine Encephalitis Virus and Vaccines

Venezuelan equine encephalitis virus (VEEV) is an alphavirus related to CHIKV. Humans infected with VEEV develop a febrile illness, often with severe headache, averaging 1–5 days after exposure. Dissipation of febrile illness coincides with the production of neutralizing antibodies. The average case fatality rate of VEEV is <1%. Children who have more severe disease are more likely to develop encephalitis and can be left with severe neurological complications.

VEEV has been recognized as a potential biological weapon because of its high attack rate with a debilitating illness and its adaptability to aerosol dissemination. Accordingly, the US Army has invested much research in this pathogen and developed experimental vaccines to protect those who handle VEEV in the laboratory (Wolfe 2013).

Two vaccines for VEEV administered to laboratory workers at US Army Medical Research Institute for Infectious Disease (USAMRIID) under Investigational New Drug (IND) are a live attenuated virus vaccine (TC83) and an inactivated virus vaccine (TC84). TC83 is the most widely used but has a significant (26%) non-response rate. Non-responders who require immunity are generally offered the inactivated TC84 vaccine. Laboratory workers at USAMRIID may have also received investigational formalin-inactivated vaccines for Eastern

Equine Encephalitis (EEEV) and/or Western Equine Encephalitis (WEEV) Viruses (Reisler 2012).

1.1.3. Alphavirus Immune Interference

Over the many decades of experience with alphavirus vaccines at USAMRIID a number of studies have demonstrated immune responses to an alphavirus vaccine may be impaired among individuals who previously received a vaccine for a heterologous alphavirus. This phenomenon has been dubbed “alphavirus immune interference”. While antibody responses to chikungunya were impaired in studies of prior recipients of TC83, there is no evidence that the non-responders were more susceptible to chikungunya. Challenge studies, though not consistently showing cross-protection, also do not show evidence that clinical outcomes are worse in prior recipients of heterologous alphavirus vaccines (Jochim 1974) or experimental infections (Byrne 1964).

1.2. Name and Description of Investigational Vaccine

PXVX0317 is the Sponsor’s research name for this Chikungunya Virus-Like Particle Vaccine (CHIKV-VLP vaccine). PXVX0317 is a field-formulated vaccine with two components: CHIKV-VLP and Alhydrogel® adjuvant. The final concentration of the CHIKV-VLP is 40mcg per dose. CHIKV-VLP is essentially identical to the VRC-CHKVLP059-00-VP vaccine used in the nonclinical studies. Alhydrogel is a 2% (w/w) aqueous suspension of aluminum hydroxide.

1.3. Study Objectives

The goal of this study is to evaluate the safety and immunogenicity of the chikungunya vaccine candidate PXVX0317 when administered to prior recipients of experimental alphavirus vaccines versus alphavirus naïve gender and age-matched controls.

Safety Objectives

The primary safety objective is to evaluate the safety of PXVX0317 when administered to prior alphavirus vaccine recipients versus gender and age-matched controls. Safety will be assessed by measuring the incidence of local and systemic solicited adverse events (AEs), unsolicited AEs, and serious adverse events (SAEs).

Immunogenicity Objectives

Primary

- To evaluate the neutralizing antibody response to CHIKV induced by PXVX0317 when administered to prior alphavirus vaccine recipients versus gender and age-matched controls.

Secondary

- To evaluate the overall antibody responses to CHIKV and VEEV induced by vaccination with PXVX0317 when administered to prior alphavirus vaccine recipients versus gender and age-matched controls.

Exploratory

[figure not shown]
- To evaluate the cellular immune response to CHIKV induced by vaccination with PXVX0317 when administered to prior alphavirus vaccine recipients versus gender and age-matched controls.
- To evaluate the humoral immune responses to EEEV and WEEV induced by vaccination with PXVX0317 in selected subjects who previously received these vaccines versus alphavirus-naïve controls.

1.4. Study Design

This is a Phase 2 parallel-group, open label study in healthy adults 18-65 years of age. A total of 60 subjects are planned to be enrolled with up to 30 at each of two sites. Subjects who have previously received an investigational heterologous alphavirus vaccine and are enrolled at USAMRIID will be matched by age (± 3 years) and gender (both birth and self-identified) with alphavirus-naïve subjects enrolled at Walter Reed Army Institute of Research (WRAIR). This matching is done to ensure that demographic characteristics are comparable between the groups, not to pair data between two specific individuals.

This study has a screening period of 60 days, a treatment and observation period from Day 1 to Day 29, and a follow-up period through Day 182 (± 14 days) (Figure 1).

Figure 1: EBSI-CV-317-002 Study Schema

Study Duration

The maximum possible study duration for an individual subject is 256 days.

Inclusion Criteria:

1. Age 18 to 65 years old (inclusive)
2. For women of childbearing potential, a negative pregnancy test at screening and on vaccination day, practicing highly effective contraception for at least 30 days prior to vaccination, and willing to use a highly effective method of contraception through study completion.
3. Able and willing to provide informed consent for study participation prior to screening procedures.
4. Free of obvious health problems as established by medical history and clinical examination at screening and enrollment.
5. Available to participate for the duration of the study (approximately 8 months).
6. For the cohort of prior alphavirus vaccine recipients, a documented history of prior alphavirus vaccination.

Exclusion Criteria:

1. Acute disease or febrile illness at the time of enrollment.
2. Clinically significant cardiac, respiratory, rheumatologic or other medical or psychiatric condition that, in the opinion of the Investigator, places the subject at increased risk or affects their ability to understand and comply with study procedures.
3. Abnormal screening lab test results that, in the opinion of the investigator, obscures interpretation of the safety data or suggests a clinically significant cardiac, respiratory, rheumatologic or other medical condition that places the subject at increased risk.
4. Pregnant, lactating or planning to become pregnant during the study period.
5. Laboratory evidence of infection with Hepatitis B, C or HIV.
6. History of naturally (non-laboratory) acquired chikungunya or other alphavirus infection or travel to a WHO-designated chikungunya-endemic region within 30 days prior to Day 1.
7. History of acute allergic reaction to any component of CHIKV-VLP vaccine, or Alhydrogel®.

8. Current (30 days prior to Day 1) or anticipated use of systemic immunomodulatory or immunosuppressive medications.
9. History of splenectomy, immunosuppressive condition, autoimmune disease, or immunodeficient condition.
10. Family history of congenital or hereditary immunodeficiency.
11. Suspected or known current alcohol abuse that, in the opinion of the investigator, would interfere with their ability to understand and comply with study procedures.
12. Current intravenous drug use.
13. Prior receipt of an investigational chikungunya vaccine.
14. Receipt or planned receipt of any licensed vaccine from 30 days prior to Day 1 through the Day 29 study visit.
15. Participation in another clinical trial during the study period in which an investigational product is administered.
16. For the alphavirus naïve group, history of prior alphavirus vaccination is exclusionary.

Study Procedures

After signing the informed consent form, subjects will undergo screening procedures up to 60 days before the first injection. Subjects will be observed in clinic for 30 to 60 minutes after injection. Local and systemic solicited events occurring within 7 days after the injection will be recorded by the subject using a memory aid. Subjects will be specifically asked to record local injection site events (pain, redness, and swelling) and systemic events (fever with oral temperature ≥ 100.4 °F, chills, fatigue, malaise, headache, myalgia, arthralgia, and nausea). Any other AEs and medications used through Day 29 will also be recorded. The reporting period for SAEs begins at the time of informed consent and continues for the duration of study participation. Concomitant medications associated with an SAE will be collected through the end of the study. Blood will be collected at Day 1 (before the injection) and Days 8, 22, 29, 57 and 182. See Table 1 on the following page for the complete schedule of study procedures and events.

Table 1: Schedule of Events

Study Event ¹	Screen	Day 1	Day 8	Day 22	Day 29	Day 57	Day 113	Day 182	Early DC
Compliance Ranges	-60 to -1	NA	+3 days	±3 days	±3 days	±7 days	±10 days	±14 days	
Informed Consent	X								
Vital signs	X	XX ⁸	X	X	X	X ⁹	X ⁹	X ⁹	
Review Inclusion/Exclusion Criteria	X	X							
Screening Medical History to include prior/concomitant medications	X								
Physical Examination	X								
Interim medical history, solicited ² and unsolicited ³ AEs, and concomitant medications		X	X	X	X				X
Memory aid distribution		X							
Memory aid collection and review			X						If < D8
Clinical check ⁴		XX ⁸	X	X	X	X	X	X	X
CBC ⁵	X	X	X						If < D8
Creatinine, AST, ALT ⁵	X	X	X						If < D8
Anti-HIV-1/2, Anti-HCV, HBsAg, HBcAb, HBsAb	X								
Urine pregnancy test ⁶	X	X			X				If < D29
Sera for antibody assays/future use ⁷		X	X	X	X	X		X	X
Collection of blood for Peripheral Blood Mononuclear Cells (PBMCs)		X	X		X	X		X	
Minimum volume of blood required	24.5 mL	84.5 mL	84.5 mL	17 mL	57 mL	77 mL	0 mL	77 mL	0 to 20 mL
Cumulative volume of blood required (approximate mL)	30	120	210	230	290	370	370	450	n/a
Vaccination		X							

¹ SAEs will be collected throughout the study

² Solicited AEs collected through Day 8 only.

³ Unsolicited AEs collected through Day 29 only.

⁴ Clinical checks: targeted physical exams based on AEs/SAEs identified

⁵ CBC, Creatinine, AST, ALT will be collected but the results will not be included in the database.

⁶ Urine pregnancy tests only for women of child-bearing potential.

⁷ Antibody assays vary with time point but include NT80 to CHIKV, PRNT80 to VEEV, total antibodies to CHIKV and VEEV, and exploratory assays of humoral immunity.

⁸ On vaccination day, vital signs and clinical checks will occur twice: before and 30 to 60 minutes after vaccination.

⁹ Vital signs may be collected at the discretion of the investigator past Day 29 but will not be included in the database.

1.5. Sample Size and Power

The sample size here was chosen based on the number of subjects in the Fort Detrick Special Immunization/Special Procedures Program (USAMRIID) who are available for screening. Of the approximately 60 available, 30 are expected to enroll in this trial along with an equal number of alphavirus naïve age- and gender-matched subjects. Based on an interim analysis of this vaccine lot and regimen in Study PXVX-CV-317-001, at least 95% of the alphavirus-naïve controls are expected to seroconvert in this trial. Assuming that the alphavirus-naïve group has a 95% seroconversion rate, a total sample size of 60 subjects affords 80% power to detect a significant difference between groups if the seroconversion rate in the prior alphavirus vaccine recipients is 65% or less. Or, in other words, power is 80% to detect a difference between groups if the seroconversion rate in the prior alphavirus recipients is 30 percentage points lower than in the alphavirus-naïve group. Compared to the previously cited studies in which decrements in the proportion of seroconversion of 64% (McClain 1998) and 100% (Harrison 1971) (DeMeio 1979) were seen, this study is adequately powered to detect immune interference on the order of one-half to one-third of what has previously been described. Further details of sample size and power estimation can be found in Section 9.1 of the protocol.

2. TYPE OF PLANNED ANALYSIS

This analysis plan describes the methods by which the data from this study will be analyzed. Completion of the Day 182 assessment for the final subject will mark the end of electronic data capture (EDC) data collection for the study. A final analysis of data collected throughout the study from all subjects will be performed after the last subject has completed the study and the immunogenicity and safety data have been locked. No interim analysis is planned for this study.

3. GENERAL CONSIDERATIONS FOR DATA ANALYSES

Continuous variables will be summarized in terms of the sample size, mean, standard deviation, median, minimum and maximum. The geometric mean and 95% confidence interval (CI) will be presented as appropriate. Calculation of the geometric mean will be performed by exponentiating the mean of the \log_{10} -transformed data to convert to the non-transformed scale. The calculation of the corresponding 95% CI will be performed in a similar manner. Categorical variables will be summarized using frequency counts and percentages. In general, data will be summarized by study arm (prior alpha vs. naïve alpha) and overall. Unless otherwise noted, the denominator for the percentages will include all subjects in the respective study arm.

The minimum and maximum values will be presented with the same number of decimal places as the raw data collected. The mean, median, standard deviation, and standard error will be presented using one additional decimal place.

For subject counts/frequencies, percentages will generally be shown to one decimal place. The denominator will be the total size of the sample, N, unless otherwise noted. Counts of 0 will be shown but 0% will be shown as blank. A percentage of 100% will be reported as 100%.

3.1. Analysis Populations

Analysis populations define which subjects are included in an analysis. A summary of the number and percent of subjects in each analysis population will be provided by study arm and in total.

3.1.1. Enrolled Population

The enrolled population, referred to as the study population in the protocol, is comprised of all screened subjects who provide informed consent and provide demographic and other baseline screening measurements, and are assigned a study subject identification (ID) number.

3.1.2. Exposed Population

All subjects in the enrolled population who receive study vaccination.

3.1.3. Safety Population

All subjects in the enrolled population who receive study vaccination and provide safety assessment data. This generally includes anyone who was not lost to follow-up at Day 1 as they will be at risk for reporting an SAE.

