9.4 Populations for Analysis

Study Population: All screened subjects who provide informed consent and provide demographic and other baseline screening measurements, and are assigned a study subject ID.

Exposed Population: All subjects in the Study Population who receive study vaccination.

Safety Population: All subjects in the Exposed Population who provide safety assessment data. This generally includes anyone who was not lost to follow-up at Day 1 as they will be at risk for reporting an SAE.

Immunogenicity Evaluable Population (IEP): The IEP includes all subjects in the Exposed Population who:

- Have no important protocol deviation or other reason to be excluded as defined prior to database lock.
- Have not received a prohibited medication.
- Provide evaluable serum sample results for baseline, the relevant post-vaccination time points, and within the required time frames:
 - Baseline: Day 1 or within 60 days before study vaccine administration
 - Day 22: Day 19 through Day 25, inclusive

Analysis of demographic and baseline characteristics: The demographic and baseline characteristics will be summarized according to prior alphavirus vaccine exposure group and overall.

Age, height, weight, and body mass index at enrollment will be summarized by reporting the mean, standard deviation, median, minimum and maximum, and calculated by prior alphavirus vaccine exposure group and overall.

The frequencies and percentages of subjects by sex, race, and ethnicity will be presented by vaccine exposure group and overall. Demographic data will be tabulated for the Study, Immunogenicity Evaluable, and Safety populations.

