9.5.1 Solicited AEs

With the exception of redness and swelling, all solicited AEs will be summarized according to severity grading scales defined in [Section 6.2](#) from “mild” to “potentially life-threatening.”

Solicited AEs will be recorded daily until 7 days post-injection using a structured memory aid. The analyses of solicited AEs (any event, after any injection, and after each injection) will be performed by maximum severity and by treatment group. In addition, solicited AEs ongoing after 7 days post-injection will also be recorded as unsolicited AEs.

Summary tables tallying the incidence, timing, duration and severity of any local or systemic solicited AE will be presented. The pre-exposure groups will be compared on the incidence of each type of solicited AE using pairwise Fisher’s exact tests. The percentage of subjects experiencing each solicited AE will also be presented by maximum severity.

The severity of redness and swelling recorded as diameters (mm) will be summarized according to categories based on the largest diameter linear measurement when the local reaction is present:

- Grade 0/absent = 0 to 24 mm.
- Grade 1/mild >24 to \leq 50 mm.
- Grade 2/moderate >50 to \leq 100 mm
- Grade 3/severe >100 mm or <100 mm with blister formation or skin breakdown

Events reported as not present (0 mm is entered) will be reported as Grade 0.

The following classifications are used in the summaries:

Grade 0 (0-24 mm), Any (>24-50 mm, >50-100 mm, >100 mm)

The following summaries of solicited events will be performed:

1. Solicited events by day post-injection, for each event and for any event.
2. Time of first onset of solicited adverse events, after injection, for each event and any event.
3. Solicited adverse events by maximum event severity, after injection, for each event and for any event.
4. Duration of solicited adverse events (defined as the number of total days during the post-vaccination collection period with the event), after injection, for each event and any event.
5. Solicited adverse events, occurrence of at least one event by category (local, systemic), after injection.

For each of the time points or time intervals presented in the summaries, only subjects with at least one observation (i.e., any non-missing values but excluding “Not done/unknown”) for the solicited adverse events will be summarized.

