7. SAFETY ANALYSES

7.1. Extent of Exposure

Vaccine administration data, including date/time of vaccination and injection site location, will be provided in a listing for all subjects in the exposed population.

All safety analyses will be based on the safety population.

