7.3.1. Analysis Methods for Safety Endpoints

The number and percentage of subjects who experience a solicited AE recorded during Days 1 through 8 will be summarized according to maximum severity grade by study arm and decreasing total frequency. For subjects with multiple events of the same type, only the event of the highest severity will be counted in each summary. Events with missing severity grades will be handled according to Section 7.1.1. A Fisher's exact test will be used to compare the frequency of the corresponding solicited event between the two groups. The 95% CI for the subject percentages will be calculated using the Wilson method. This summary will be repeated for treatment-related solicited AEs and solicited AEs during Days 1 through 8 of at least severe (Grade 3) severity or higher.

Day of onset post-injection will be summarized with descriptive statistics for each type of solicited AE by study arm. The median and its 95% CI will be estimated by Kaplan-Meier analysis. The log-rank test will be used to compare day of onset between the two study arms. This summary will be repeated for treatment-related solicited AEs.

The number of days a subject experiences each solicited AE will be summarized by descriptive statistics (number of subjects with each solicited AE, mean, median, minimum and maximum) by study arm. The days may not be consecutive. The 95% CI of the mean will be based on t-statistics assuming a normal distribution. The 95% CI of the median will be a distribution-free estimate based on order statistics. A Wilcoxon rank sum test on the number of days of symptoms will be used to compare both groups. This summary will be repeated for treatment-related solicited AEs.

The percentage of subjects reporting solicited AEs will also be summarized for each event category and sign and/or symptom by study arm and day on study.

A summary of the number and percentage of subjects who experience an unsolicited AE during Days 1 through 29 by SOC and PT will be presented. Similarly, a summary of the number and percentage of subjects who experience a treatment-related AE during Days 1 through 29 by SOC and PT will be provided.

In addition, a summary of the number and percentage of subjects who experience an SAE during Days 1 through 182 by SOC and PT will be presented. Similarly, a summary of the number and percentage of subjects who experience a treatment-related SAE during Days 1 through 182 by SOC and PT will be provided.

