14.3.1.1	Solicited Events by Highest Reported Severity- Safety Population
14.3.1.2	Solicited Events of at Least Severe (Grade 3) Severity- Safety Population
14.3.1.3	Treatment-related Solicited Events by Highest Reported Severity- Safety Population
14.3.2.1	Day of Onset for Subjects who Reported Solicited Events- Safety Population
14.3.2.2	Day of Onset for Subjects who Reported Treatment-related Solicited Events - Safety Population
14.3.3.1	Number of Days with Symptoms for Subjects who Reported Solicited Events- Safety Population
14.3.3.2	Number of Days with Symptoms for Subjects who Reported Treatment-Related Solicited Events - Safety Population
14.3.4	Percentage of Subjects with Solicited Events by Day on Study- Safety Population
14.4.1	Listing of Serious Adverse Events Leading to Death - Safety Population
14.4.2	Listing of Serious Adverse Events - Safety Population
14.4.3.1	Serious Adverse Events by System Organ Class and Preferred Term - Safety Population
14.4.3.2	Treatment-related Serious Adverse Events by System Organ Class and Preferred Term - Safety Population
14.4.4.1	Unsolicited Adverse Events by Preferred Term in Descending Order of Incidence Through Day 29 - Safety Population
14.4.4.2	Unsolicited Adverse Events of Severe or Higher Severity by Preferred Term in Descending Order of Incidence Through Day 29 - Safety Population
14.4.5.1	Unsolicited Adverse Events Through Day 29 by System Organ Class and Preferred Term - Safety Population
14.4.5.2	Solicited and Unsolicited Adverse Events Through Day 29 by System Organ Class and Preferred Term - Safety Population
14.4.5.2.1	Solicited and Unsolicited Adverse Events Through Day 29 by System Organ Class and Preferred Term by Race - Safety Population
14.4.5.2.2	Solicited and Unsolicited Adverse Events Through Day 29 by System Organ Class and Preferred Term by Gender - Safety Population
14.4.6	Unsolicited Adverse Events Through Day 29 by System Organ Class, Preferred Term, and Highest Reported Severity - Safety Population

Table	Title
14.4.7	Unsolicited Adverse Events Leading to Withdrawal by System Organ Class and Preferred Term - Safety Population
14.4.8	Treatment-related Unsolicited Adverse Events by Preferred Term in Descending Order of Incidence Through Day 29 - Safety Population
14.4.9.1	Treatment-related Unsolicited Adverse Events Through Day 29 by System Organ Class and Preferred Term - Safety Population

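### SAP 7.3.1 omits the protocol 9.5.1 denominator rule for solicited events, so under the SAP's default an unobserved subject or day counts as a non-event

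*SAP*

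**What the plan says.** **Protocol.** Section 9.4 defines the Safety Population as "All subjects in the Exposed Population who provide safety assessment data", and Section 9.5 uses it for all safety analyses. For solicited events Section 9.5.1 adds a restriction: "For each of the time points or time intervals presented in the summaries, only subjects with at least one observation" enter the summary. Entries marked as not done or unknown do not count as observations.

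**SAP.** Section 3.1.3 defines the same population: "All subjects in the enrolled population who receive study vaccination and provide safety assessment data". It adds the same explanation as the protocol: "This generally includes anyone who was not lost to follow-up at Day 1 as they will be at risk for reporting an SAE". Section 7.1 states: "All safety analyses will be based on the safety population". On solicited events, Section 7.3.1 says: "The number and percentage of subjects who experience a solicited AE recorded during Days 1 through 8 will be summarized", by maximum severity and study arm, with Wilson 95% intervals. It adds that a Fisher's "exact test will be used to compare the frequency of the corresponding solicited event between the two groups". Table 14.3.1.1 is titled "Solicited Events by Highest Reported Severity- Safety Population".

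SAP 7.3.1 contains no counterpart to the 9.5.1 restriction. SAP Section 8, which records changes from the protocol's methods, does not mention it. SAP Section 3 sets a general default: percentages are taken over all subjects in the arm unless noted otherwise. Addendum 2 reruns the solicited-event tables and states no denominator.

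**The concern.** Someone programming from the SAP finds a Safety Population table, a default denominator of the whole arm, and nothing in 7.3.1 that overrides it. A vaccinee with no solicited observation for Days 1 to 8 then adds one to the denominator and nothing to the numerator. In the percentage and in the Fisher table that is the same as an observed absence of the event. In by-day Table 14.3.4, each day without a record is treated as symptom-free in the same way.

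Solicited reactions are the safety outcomes that the plan tests between arms. The bias is always downward. Prior recipients are enrolled at USAMRIID and naïve controls at WRAIR, so arm and site coincide. If the sites differ in how completely they obtain solicited data, that difference would appear as a difference in reactogenicity between arms.

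**Working it through.** **1. The plan's own safety figures.** Protocol 9.1 states 80% power for a 30-point difference when one group has a 5% rate, and a 95% chance of seeing a 5% event at least once among 60 subjects.
- Exact enumeration of Fisher's test with 30 versus 30, 5% versus 35%, gives 78.8%, within 2 points of the stated 80%. It uses two-sided 0.05, which protocol 9.6 states for immunogenicity and which is assumed here for safety.
- 1 − 0.95^60 = 95.4%, against 95% stated.

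Both reproduce with complete data. The denominator question changes neither stated design figure.

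**2. The texts side by side.**
- Analysis population: the same in protocol 9.4/9.5 and SAP 3.1.3/7.1.
- Restriction to subjects with an observation: present in protocol 9.5.1, absent from SAP 7.3.1.
- Fallback denominator: SAP Section 3, all subjects in the arm.
- Declared as a change: no (SAP Section 8).

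The gap therefore lies in SAP 7.3.1 read with Section 3, not in the population definition.

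**3. Effect on the displayed rate.** Let m be the number of unobserved subjects in an arm of 30. No document gives m, so the values are assumptions. With true rate p among all 30, the expected displayed rate is p × (30 − m)/30 if they stay in the denominator and p if they are excluded, assuming missingness is unrelated to the event. The rates come from protocol 1.2.2.3, which reports any injection across several regimens, so they are illustrative.

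| m | Pain, true 41.4% | Shortfall (41.4 × m/30) | Headache, true 27.2% |
|---|---|---|---|
| 1 | 40.0% | 1.4 points | 26.3% |
| 3 | 37.3% | 4.1 points | 24.5% |
| 6 | 33.1% | 8.3 points | 21.8% |

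If the missing subjects are all in one arm and the true rates are equal, the shortfall is also the expected artificial gap between arms.

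**4. Effect on the Fisher test** (exact enumeration, nominal two-sided 0.05).

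| Scenario | m | Excluded (protocol 9.5.1) | Kept in N = 30 (SAP default) |
|---|---|---|---|
| Power, 5% vs 35%, m missing in each arm | 1 | 76.6% | 76.6% |
| | 3 | 71.5% | 71.5% |
| | 6 | 70.6% | 62.3% |
| Power, 5% vs 35%, m missing in the higher-rate arm only | 3 | 83.7% | 68.7% |
| | 6 | 78.0% | 56.1% |
| False rejection, both 41.4%, m missing in one arm only | 3 | 3.28% | 3.11% |
| | 6 | 2.94% | 5.35% |
| | 9 | 3.95% | 9.83% |

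With complete data these are 78.8% power and 2.61% false rejection. Excluding a few subjects can raise power above 78.8% because the Fisher test is discrete and its true size moves with the group sizes. The comparison to read is across each row.

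**The case against.** The strongest reply is that the SAP does not change the rule but merely fails to repeat it.

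- **No sentence scores missing data as no reaction, SAP 3.2 rules out imputation, and protocol 9.5.1 is not withdrawn.** All true, and a programmer might still apply 9.5.1. But leaving a value missing while keeping the subject in N gives the same percentage as scoring a non-event, and the SAP's stated default is to keep the subject in N. Two denominators remain arguable for one table, and the SAP should settle which applies.
- **The Safety Population is the protocol's own.** This stands. A reader might infer that SAP 3.1.3 is the error and that a new analysis set is needed. The near-identical wording in protocol 9.4 does not support that; a denominator rule within the same population is enough.
- **A lost memory aid is not a lost observation.** This stands too. Under protocol 4.11 the Investigator's assessment, documented separately from the memory aid, goes on the eCRF, and staff evaluate solicited events at Day 8. A reader might infer that anyone who fails to return a diary is counted as reaction-free. That does not follow for a subject assessed at Day 8.
- **A subject who attends only Day 1 may still have an observation.** Protocol 5.1.2 includes a solicited evaluation after vaccination on Day 1. If it is recorded, that subject meets 9.5.1 for the whole interval, and the two rules may nearly coincide for overall incidence and the Fisher test. The by-day table, to which 7.3.1 assigns no test, is then the main exposure.
- **The onset and duration tables are not affected.** Tables 14.3.2.1 to 14.3.3.2 are titled for subjects who reported events, so this point should not extend to them.
- **The missing counts are assumed.** Correct. Nothing in the documents shows unequal completeness between sites.

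**Conclusion.** The point holds as an undeclared departure from a protocol analysis rule. Read as written, the SAP puts subjects or days without solicited observations into the denominator as non-events, which can only lower the reported incidence. It concerns Tables 14.3.1.1 to 14.3.1.3 and by-day Table 14.3.4.

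The size is unknown. It is zero with complete data, and about 1.4 points per unobserved subject at a 41.4% rate in an arm of 30. In the protocol's 5% versus 35% scenario, one to three missing per arm leaves power the same under either rule. The effect becomes material when missingness is larger or one-sided: with six missing in the higher-rate arm, power is 56.1% rather than 78.0%. These figures rest on assumed counts, on 30 per arm, and on missingness unrelated to the event.

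A reader might go further and conclude that the arm comparison of reactogenicity is distorted. The documents do not support that. They show that the SAP leaves the route open, not that any solicited data were missing or that the sites differed.

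**What to change.** In SAP 7.3.1 (now most easily by addendum), state that percentages, Wilson intervals and Fisher tests for solicited events use as denominator the Safety Population subjects with at least one non-missing solicited observation for that event and interval, per protocol 9.5.1. Apply this to Tables 14.3.1.1 to 14.3.1.3, and apply it day by day in Table 14.3.4. Report, by arm, the number of subjects without such data. If the whole-arm denominator is in fact intended, list and justify the departure in SAP Section 8. Leave SAP 3.1.3 unchanged and keep the full Safety Population for unsolicited events and SAEs.

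The cost is a sentence or two and a changed denominator in tables that Addendum 2 already reruns. The downside is that denominators will differ slightly between solicited and unsolicited tables, which a footnote can explain.
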